The Evaluation of D-glucose Weighted Chemical Exchange
Saturation Transfer (glucoCEST)-Based Dynamic Glucose
Enhanced(DGE) Magnetic Resonance Imaging (MRI) in
Brain Tumor

Main research unit: Zhujiang Hospital of Southern Medical University

Principal investigator: [name]

Participating units and persons in charge:

Statistical Analysis Unit:

Scheme version: 4.0

Scheme version date: December 27, 2019

Confidentiality statement

The ownership of all information contained in this study protocol belong to the investigator of the project. It is provided only for review by the ERC and relevant agencies. It is prohibitive that disclose any information to third parties unrelated to the study without the written consent of the Principal Investigator (PI).

Catalog

Abstract.....	4
Background	6
Materials and Methods.....	7
Patients:	7
Inclusion Criteria:	7
Exclusion Criteria.....	7
Methods.....	8
.....	8
Methods of DGE	8
Statistic Analysis.....	9
Statistic tools: SPSS 23.0.....	9
Basic principles:	9
Missing data:	9
Description statistics:.....	9
Baseline data analysis:.....	9
Analysis of influencing factors:.....	10
Ethical considerations.....	10
References:.....	10

Abstract

Subject	Application of glucose CEST MR imaging in brain tumors
Sponsor	Department of Imaging Diagnosis, Zhujiang Hospital, Southern Medical University
Research Institutes	Zhujiang Hospital, Southern Medical University
Principal Investigator	[name]
Purpose	Whether glucose CEST MR imaging is superior to gadolinium contrast agents based MR imaging in brain tumors
Hypothesis	Glucose CEST MR imaging is more effective than gadolinium contrast imaging in the diagnosis of brain tumors
Design	Clinical trial
Sample Capacity	100
Inclusion and Exclusion Criteria	
Minimum Age: 18 Years
 
Maximum Age: 75 Years
 
Criteria:
 
Inclusion Criteria:
 
(1) Patient must have a brain mass consistent with a primary brain tumor or metastatic brain tumor(2) able to give consent (3) willingness to participate in this
 
Exclusion Criteria:

	
1) presence of any ferromagnetic implant (cardiac pacemakers, aneurysm clip, etc.) (2) pregnancy (3) claustrophobia or anxiety disorder (4) history of vertigo (5) persons with diabetes mellitus (self-report or HbA1C \geq 6.5%) (6) Sickle cell disease (7) persons taking prescription medicine for hypertension (8) blood iron deficiency (Hb concentration $<$ 11 g/dL or Hct $<$ 32%) (9) If volunteering for MRI: history of kidney disease and/or eGFR $<$ 60. (10) Middle-ear disorder (11) double vision (12) Seizure disorder (13) Multiple myeloma (14) Solid organ transplant (15) History of severe hepatic disease/liver transplant/pending liver transplant

Interference	MR Imaging based on DGE
Measure	The area of hyperintense and the AUC between 2-5min of DGE
Patients	brain tumor patient treated at Zhujiang Hospital of Southern Medical University
Statistical Method	Differential test and Consistency analysis were used for statistical analysis

Background

The priority treatment of brain tumor is surgical resection. Recurrent malignant glioma is the most common and highly malignant primary brain tumor in adults. It mainly includes the pleomorphic glioblastoma (GBM) and anaplastic astrocytoma (AA). The average survival period of GBM is only 14.6 months [1], while the average lifetime of AA is only 2 to 3 years [1, 2]. Residual tumor and highly recurrence rate is the main reason. Besides, the feasibility of reoperation is extremely low. Moreover, progression-free survival (6-month progression-free survival (6M-PFS)) was only 15-21% of patients with recurrent glioma. The response rate of conventional chemotherapy was less than 15% in patients with recurrent glioma [1, 2]. Therefore, accurate clinical assessment of tumor scope is of great significance for GBM expansion surgery to remove the potential tumor immersed area and improve the survival rate of patients.

Recently, natural D-glucose suggested as a potential biodegradable contrast agent. The feasibility of using D-glucose for dynamic perfusion imaging explored to detect malignant brain tumors based on the breakdown of blood brain barrier (BBB)[3]. Our study try to evaluate the feasibility of dynamic glucose enhanced(DGE) magnetic resonance imaging (MRI) in brain tumor, which based on D-glucose weighted chemical exchange saturation transfer (glucoCEST).

In 2015, Xiang Xu et al. first demonstrated the feasibility of DGE MRI in four normal volunteers and three glioma patients [4]. Routinely, D-glucose was used in human biochemical studies. The objective of this study was to evaluate the feasibility of DGE for visualizing BBB permeability in brain tumor models and to compare it with GBCA-based DCE for visualizing BBB permeability.

With glucose CEST MR imaging, we attempt to accurately predict the grade of brain glioma and to evaluate the infiltration range of tumor cells in the edema zone around glioma, so as to provide a more sufficient basis for the formulation of surgical resection plan for patients.

Materials and Methods

Patients:

Brain tumor patient treated at Zhujiang Hospital of Southern Medical University.

Minimum Age: 18 Years

Maximum Age: 75 Years

[figure not shown]
Inclusion Criteria:

(1) Patient must have a brain mass consistent with a primary brain tumor or metastatic brain tumor (2) able to give consent (3) willingness to participate in this

Exclusion Criteria:

(1) Presence of any ferromagnetic implant (cardiac pacemakers, aneurysm clip, etc.) (2) Pregnancy (3) Claustrophobia or anxiety disorder (4) History of vertigo (5) Persons with diabetes mellitus (self-report or HbA1C \geq 6.5%) (6) Sickle cell disease (7) Persons taking prescription medicine for hypertension (8) Blood iron deficiency (Hb concentration $<$ 11 g/dL or Hct $<$ 32%) (9) If volunteering for MRI: history of kidney disease and/or eGFR $<$ 60. (10) Middle-ear disorder (11) double vision (12) Seizure disorder (13) Multiple myeloma (14) Solid organ transplant (15) History of severe hepatic disease/liver transplant/pending liver transplant.

Methods

Methods of DGE

Time-resolved glucose signal changes were detected using chemical exchange saturation transfer (glucoCEST) MRI. Dynamic glucose enhanced (DGE) MRI was used to measure tissue response to an intravenous bolus of D-glucose. Starting the dynamic glucose scan, 3 minutes later, a brief hyperglycemic state was established by intravenous infusion of hospital-grade D50 glucose (D50, 25 g of dextrose in 50 mL of water sterile solution), followed by 20 mL of saline solution in 1 arm. The glucose infusion was performed using a power injector at an infusion rate of 0.2 mL/s, corresponding to total infusion times of 250 seconds. Performing dynamic contrast enhancement based on Gd-DTPA in 30 minutes later, which was used for comparison as golden standard. Dose of agent is according to the proportion of 0.2ml/kg body weight. The Gd-DTPA infusion was performed using a power injector at an infusion rate of 3 mL/s, followed by 20 mL of saline solution in 1 arm.

Statistic Analysis

Statistic tools: SPSS 23.0

Basic principles:

All statistical inferences were tested by bilateral tests, the test level of statistical significance was set at 0.05, and the confidence interval of parameters was estimated by 95% confidence interval. The parametric method is used as far as possible. When the data does not meet the parametric method conditions, the data transformation method can be used to make it meet the conditions. If the data still does not meet the parameter method conditions, the non-parametric method can be considered.

Missing data:

The case data that did not meet the statistical requirements were excluded.

Description statistics:

The mean, standard deviation and confidence interval are given for measurement data. The minimum, maximum, P25, median and P75 are given if necessary. The mean and standard deviation of the trip value were calculated from paired measurement data. Median and mean rank are given when nonparametric methods are used. The enumeration data give the frequency distribution and the corresponding percentages. Rank data give frequency distributions and corresponding percentages, as well as median and mean rank. The positive rate, positive number and the number of cases in the denominator were given in qualitative data.

Baseline data analysis:

Descriptive analysis of baseline data, including baseline levels of endogenous glucose CEST in brain tissue.

Analysis of influencing factors:

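### The Hypothesis claims better diagnosis of brain tumours, but everyone enters with a known mass and the measures are not scored against tumour status, so a detect-or-exclude claim cannot be supported.

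*Protocol*

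**What the plan says.** - **Claim.** The Abstract's Hypothesis is "Glucose CEST MR imaging is more effective than gadolinium contrast imaging in the diagnosis of brain tumors". The Purpose row likewise asks about superiority over gadolinium-based imaging.
- **Who enters.** The first inclusion criterion, in the Abstract and again under Materials and Methods, is "Patient must have a brain mass consistent with a primary brain tumor or metastatic brain tumor". The Patients section describes the population as "Brain tumor patient treated at Zhujiang Hospital of Southern Medical University". No healthy or non-tumour group is named.
- **What is measured.** The Abstract's Measure row gives "The area of hyperintense and the AUC between 2-5min of DGE". Because it is tied to a time window, this AUC reads as the area under a signal-time curve, not under an ROC curve.
- **How it is compared.** The Statistical Method row names a difference test and an agreement analysis. Under Methods of DGE, the Gd-DTPA scan is the one "which was used for comparison as golden standard".
- **Narrower aims.** The Background adds a comparison with DCE for showing blood-brain barrier permeability. It also says that "we attempt to accurately predict the grade of brain glioma and to evaluate the infiltration range of tumor cells in the edema zone around glioma".
- **Size.** The row "Sample Capacity" gives 100, without a derivation.

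**The concern.** Read as a question of tumour or no tumour, diagnosis needs cases in which the right answer is no, and a measure that counts right and wrong answers. The entry criterion supplies such cases only by chance, and the measures record signal without reference to tumour status. A difference test can show that two bright areas differ, and an agreement analysis can show that they match. Neither shows that the larger or smaller area is the more correct one.

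At stake is the headline conclusion. A difference in area or AUC could be reported as support for better diagnosis when the data speak only to how a known mass is displayed. The Hypothesis, the eligibility criteria and the Measure are all fixed in the Protocol, and a later analysis plan cannot add negative cases to the sample.

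**Working it through.** **1. The plan's own figure.** The sample size of 100 cannot be reproduced. The Statistic Analysis section states that "the test level of statistical significance was set at 0.05", with two-sided tests, but the Protocol gives no power, effect size, standard deviation or rates. It also gives no sensitivity or specificity target that could be checked. What follows tests design logic, with an illustration of precision.

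**2. Claim against population.** To compare two methods on detecting or excluding tumour at patient level, one needs for each method:

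- sensitivity = true positives / patients with tumour;
- specificity = true negatives / patients without tumour.

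The planned number without tumour is 0 of 100. With a denominator of 0, specificity is undefined. A patient whose tumour left no visible mass on earlier imaging cannot enter, so detection in such patients cannot be studied either.

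**3. Claim against measures.** Hyperintense area and signal AUC are continuous quantities. The Protocol gives no rule that turns them into a positive or negative reading, and does not relate them to tumour status.

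**4. If some masses prove not to be tumour.** The entry wording is presumptive, so this can happen. The Protocol gives no rate, so the shares below are assumptions, as is an observed specificity of about 80%. The interval is the exact (Clopper-Pearson) 95% interval for x correct out of n:

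- lower limit = Beta quantile at 0.025 with parameters (x, n − x + 1);
- upper limit = Beta quantile at 0.975 with parameters (x + 1, n − x), or 1 if x = n.

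| Assumed non-tumour masses of 100 | Read correctly | 95% CI for specificity |
|---|---|---|
| 0 | – | not estimable |
| 2 | 2/2 | 16% to 100% |
| 5 | 4/5 | 28% to 99% |
| 10 | 8/10 | 44% to 97% |
| 15 | 12/15 | 52% to 96% |

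Even at 15 non-tumour masses the interval spans 96 − 52 = 44 percentage points; at 5 it spans 99 − 28 = 71.

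**5. Overall accuracy would not help.** A reading that calls every scan positive has 100% sensitivity and accuracy equal to 1 minus the non-tumour share: 1 − 0.05 = 95% with 5 such masses, and 1 − 0.15 = 85% with 15.

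**6. What remains estimable.** With about 100 tumours, sensitivity could be estimated usefully against an independent reference. For example, 90/100 gives a 95% CI of 82% to 95%. The weakness lies in the missing negatives, not in the number of tumour patients.

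**The case against.** The strongest reply is that diagnosis need not mean tumour versus no tumour. The Protocol does not define it so, and the Background names glioma grade and infiltration of the oedema zone. Both are diagnostic questions asked within people who have a tumour, where lower-grade lesions or oedema free of tumour cells are the negatives. Patients with a known mass are also the intended users if the purpose is surgical planning. This stands. A reader might infer that the Hypothesis is unanswerable whatever reference is used, and the document does not support that: with an independent reference such as histology, grade, extent and paired sensitivity could all be compared. As written, the reference is Gd-DTPA itself, which is also the comparator, so the choice of reference is a further obstacle. The reply does not rescue the Hypothesis, which names neither grade nor extent as its task.

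Three other inferences also go too far:

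- **That there will be no tumour-free cases at all.** The criterion asks for a mass consistent with tumour, not a confirmed one. None are enrolled by design; some may enter by chance.
- **That the plan rewards brighter images.** No section says that a larger area or AUC counts as better, and excess DGE area could worsen agreement with Gd-DTPA. A scoring rule may stand in a statistical analysis plan that is not at hand.
- **That the trial could never show tumour missed by earlier imaging.** This holds for patients with no visible lesion. Further metastases, or infiltration beyond the visible mass, could still be examined in enrolled patients.

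It is also fair to say that the Protocol plans no specificity or accuracy endpoint. The intervals above therefore show what the sample could support, not a fault in a planned analysis.

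**Conclusion.** The point holds in a limited form. The Hypothesis claims superiority in diagnosis, while the population is restricted to patients with a known mass and the measures are not scored against tumour status. The trial cannot support a claim that DGE is better at detecting or excluding brain tumour at patient level. Any specificity drawn from chance non-tumour cases would be very imprecise. That illustration rests on an assumed 5 to 15 such cases per 100 and an assumed observed specificity of 80%; neither figure comes from the Protocol. The conclusion about planned negatives needs neither assumption.

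The data would still be useful for comparing how the two methods display a known lesion. The change should be made, but it concerns what may be concluded and does not invalidate the study.

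**What to change.** 1. **Restate the Purpose and Hypothesis.** For example: in patients with a known brain mass, DGE and Gd-DTPA DCE differ in lesion display (visualisation of blood-brain barrier permeability, conspicuity and extent). Drop the claim of superiority in diagnosis. This agrees with the permeability comparison already stated in the Background.
2. **Add an internal control region.** On the scans already planned, place a mirrored contralateral normal-appearing region. Within each modality apply the same brightness threshold as for the lesion, and report the contralateral hyperintense area beside the lesion area. Where the mirrored tissue is itself involved, record the region as unavailable.
3. **Limit the grade and infiltration claims** to cases in which routine histology is available as an independent reference. The contralateral region does not test the peritumoural oedema zone and cannot stand in for tissue there.

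The cost is an amendment to the Protocol wording, one extra region per scan and a small amount of analysis. No new patients or procedures are needed. The downside is a narrower claim.

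### Does the 2 to 5 minute AUC window need a stated time zero before the plan can stand?

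*Protocol*

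**What the plan says.** The Measure row in the protocol Abstract is a single line: "The area of hyperintense and the AUC between 2-5min of DGE". The window is not mentioned again in the Methods or in the statistical section.

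Methods of DGE gives the timing: "Starting the dynamic glucose scan, 3 minutes later, a brief hyperglycemic state was established by intravenous infusion of hospital-grade D50 glucose". The product is described as "D50, 25 g of dextrose in 50 mL of water sterile solution" and is given at "an infusion rate of 0.2 mL/s, corresponding to total infusion times of 250 seconds", followed by a 20 mL saline flush whose rate is not stated. The same section says that DGE "was used to measure tissue response to an intravenous bolus of D-glucose".

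The Background sets the wider aim for DGE, which is "to compare it with GBCA-based DCE for visualizing BBB permeability". The Baseline data analysis paragraph plans a description of endogenous glucose CEST levels in brain tissue.

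**The concern.** A numeric window without an origin is only half a definition. Here the scan clock runs 3 minutes ahead of the glucose, and the window is itself 3 minutes long. Moving the origin from scan start to infusion start therefore replaces the whole window instead of shifting it slightly.

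Two analysts could each report an AUC from 2 to 5 minutes and have used different stretches of the same curve, at different stages of glucose delivery. If minutes are counted from scan start, the first 60 s of the window come before any glucose and cannot carry a response. They would add noise to a baseline-subtracted integral, or endogenous signal to a raw one.

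The AUC is one of only two stated measures, and an open origin could in principle be settled after the curves have been seen.

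**Working it through.** **Inputs**

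- Window: 2 to 5 min, i.e. 120 to 300 s after an unstated zero (Abstract, Measure row).
- Delay from scan start to glucose: 3 min = 180 s (Methods of DGE).
- Glucose volume 50 mL, rate 0.2 mL/s, stated duration 250 s (Methods of DGE).

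**Step 1: the protocol's own figure.** Volume / rate = 50 / 0.2 = 250 s, which agrees with the stated duration.

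**Step 2: glucose on the scan clock.** The infusion runs from 180 s to 180 + 250 = 430 s (3:00 to 7:10). Volume given by time t is 0.2 x (min(t, 430) - 180) mL, and zero before 180 s.

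**Step 3: the window under each origin**

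| Origin | Window on scan clock | Before glucose | During infusion | After infusion | mL given, open to close |
|---|---|---|---|---|---|
| Scan start (0 s) | 120-300 s | 60 s | 120 s | 0 s | 0 to 24 |
| Infusion start (180 s) | 300-480 s | 0 s | 130 s | 50 s | 24 to 50 |
| Infusion end (430 s) | 550-730 s | 0 s | 0 s | 180 s | 50 to 50 |

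At 300 s the volume is 0.2 x (300 - 180) = 24 mL.

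**Step 4: overlap.** Each pair of windows overlaps by 0 s. Two limits apply:

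- The first two windows meet at 300 s and frame length is not stated, so a frame at that instant could count in both.
- The end of the saline flush is a conceivable fourth origin, and its window overlaps the infusion-end window. At an assumed 0.2 mL/s the flush takes 20 / 0.2 = 100 s, the window is 650-830 s, and the overlap is 730 - 650 = 80 s. At an assumed 3 mL/s the flush takes about 6.7 s, the window is about 557-737 s, and the overlap is about 173 s.

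**Step 5: cost of the 60 s before glucose, scan-start reading only.** Assume independent frames of equal noise.

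- *Baseline = mean of 0-180 s.* The AUC over 120-300 s reduces to the integral over 180-300 s minus the integral over 0-120 s, with variance proportional to 120 + 120 = 240. Using 180-300 s alone, the variance is 120 + (120/180)^2 x 180 = 120 + 80 = 200. The SD ratio is sqrt(240/200) = 1.095.
- *Baseline treated as noise-free.* The SD ratio is sqrt(180/120) = 1.225.

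In both cases the frames before glucose contribute zero on average after baseline subtraction, so the expected AUC does not move. The comparator, 180-300 s, is a two-minute window that none of the origins in Step 3 yields. The ratios therefore bound a nuisance within one reading and do not measure the effect of choosing between readings.

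**Step 6: the texts side by side.** A 3-minute lead-in and a 2 to 5 minute window are compatible. The lead-in can supply the baseline level that the statistical section plans to describe, and the window can be counted from glucose. Since the Methods define DGE by the response to glucose, the scan-start reading, which is the only one with time before glucose, suits that purpose least.

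**The case for a change.** The strongest case for a change is that the protocol did not leave the window to another document. It wrote numeric limits for a named measure and, separately, a scan clock offset from the glucose, without joining the two. Agreeing to count from glucose does not settle the matter either, because infusion start and infusion end give windows with no common scan time (300-480 s and 550-730 s). A sentence would cure it without extra patients, scans or injections, and would stop the origin being chosen on sight of the curves.

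Much of this stands. The origin is absent from the readable text, the arithmetic is right, and one origin should be used for every patient and settled before AUC results are compared.

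It still does not amount to an error in the plan. No stated rule is wrong and no two statements conflict. The line in question is a summary row, and the operational definition of an image-derived AUC commonly sits in an analysis plan or imaging manual, neither of which is at hand.

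The link to the gadolinium comparison is also inferred. The Background compares DGE with DCE for visualizing permeability, but nothing says that the AUC, as opposed to the hyperintense area, is the quantity compared, and no DCE window is given.

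Nor would a protocol edit be quite free: Ethical considerations requires ethics committee approval before the plan is modified.

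**Conclusion.** The gap is real but narrow: a time origin is missing from a one-line summary entry. Scan-start, infusion-start and infusion-end origins give windows that share no scan time, so the origin is not trivial.

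The only harm that can be quantified, 60 s without glucose and a noise SD higher by about 10% to 22% with no shift in the expected baseline-subtracted AUC, arises solely on the reading that fits the Methods least. Those percentages rest on independent, equal-variance frames and on baseline rules that the protocol does not state. The effect of choosing infusion end over infusion start cannot be sized from the protocol, which gives no signal curve, frame length or scan length.

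Whoever extracts the AUC has the infusion timing in the Methods and can tie the window to glucose administration. This is a definition to be recorded where the extraction is specified. It is not a fault in the design or the analysis, and no change to the plan follows.

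### The protocol sets out to show that DGE diagnoses brain tumours better than gadolinium imaging, yet makes gadolinium imaging the gold standard and names no independent reference

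*Protocol*

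**What the plan says.** The Abstract gives the Purpose as "Whether glucose CEST MR imaging is superior to gadolinium contrast agents based MR imaging in brain tumors" and the Hypothesis as "Glucose CEST MR imaging is more effective than gadolinium contrast imaging in the diagnosis of brain tumors". Only the Hypothesis refers to diagnosis; the Purpose claims superiority in general terms.

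Methods of DGE describes the second scan as follows: "Performing dynamic contrast enhancement based on Gd-DTPA in 30 minutes later, which was used for comparison as golden standard".

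The Abstract's Measure entry is "The area of hyperintense and the AUC between 2-5min of DGE", and its Statistical Method entry is "Differential test and Consistency analysis were used for statistical analysis". Under Basic principles, tests are two-sided at 0.05.

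The Background sets a different objective: feasibility of DGE for showing blood-brain barrier permeability, and "to compare it with GBCA-based DCE for visualizing BBB permeability". It then adds two further aims, to predict glioma grade and to "evaluate the infiltration range of tumor cells in the edema zone around glioma". No reference is attached to either. Nowhere does the readable text name histology, biopsy, surgical findings or follow-up as a reference. One figure in Materials and Methods is not reproduced in the copy reviewed.

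**The concern.** The scan that DGE is supposed to beat is also the yardstick. Whenever the two scans disagree, a gold-standard comparison records an error by DGE, even where DGE is right. The headline hypothesis therefore has no route to confirmation.

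The practical risk lies in interpretation. Suppose DGE shows a larger hyperintense area than Gd-DTPA DCE. One author could report that DGE is more effective because it reveals more tumour; another could report that it disagrees with the gold standard. Nothing in the protocol decides between them. The Background says the imaging is meant to inform surgical resection plans, so an unsupported claim in either direction would matter.

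**Working it through.** The point is logical. The protocol gives no effect size, SD, error rate or power, so there is no figure of its own to reproduce.

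**Step 1. Accuracy with gadolinium as reference.** Let D and G be the positive/negative calls of DGE and Gd-DCE on the same unit.
- Accuracy of Gd = P(G = G) = 1.
- Accuracy of DGE = P(D = G) ≤ 1.
- In a paired comparison, the cell for DGE right and Gd wrong is always empty, so the difference DGE − Gd cannot be positive at n = 100 or any other n.

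**Step 2. The stated measures and analyses against the stated aims.**

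| Possible result | What it shows | Supports the Hypothesis? | Serves the Background comparison? |
|---|---|---|---|
| Areas differ significantly | The scans mark different amounts of tissue | No: does not say which is nearer the tumour | Yes |
| Good consistency | DGE reproduces Gd-DCE | No: agreement is not superiority | Yes |
| DGE AUC at 2-5 min | Size of the glucose signal | No: an image quantity, not a verified diagnosis | Descriptive |

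**Step 3. Illustration of how far the reference can mislead.** The protocol states no sensitivity/specificity scoring, so every input here is assumed: region-level calls, DGE truly 90%/90% (sensitivity/specificity), Gd truly 75%/90%, prevalence p of tumour regions 30%, 50% or 70%.

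P(G+) = 0.75p + 0.10(1 − p). At p = 0.5, P(G+) = 0.425 and P(G−) = 0.575.
- Errors independent given true status: apparent DGE sensitivity = (0.5×0.75×0.9 + 0.5×0.1×0.1)/0.425 = 0.3425/0.425 = 80.6%; specificity = (0.5×0.25×0.1 + 0.5×0.9×0.9)/0.575 = 0.4175/0.575 = 72.6%.
- Maximal positive dependence: 0.425/0.425 = 100%; (0.5×0.10 + 0.5×0.90)/0.575 = 0.500/0.575 = 87.0%.
- A perfect DGE: 0.375/0.425 = 88.2%; 0.450/0.575 = 78.3%.

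| p | DGE 90/90, independent errors | DGE 90/90, maximal dependence | Perfect DGE | Gd |
|---|---|---|---|---|
| 30% | 71.0% / 81.5% | 100% / 93.6% | 76.3% / 89.4% | 100% / 100% |
| 50% | 80.6% / 72.6% | 100% / 87.0% | 88.2% / 78.3% | 100% / 100% |
| 70% | 85.7% / 58.5% | 100% / 76.4% | 94.6% / 60.7% | 100% / 100% |

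DGE is truly better than Gd in every row, yet it scores below Gd in every row. At p = 0.5, a perfect DGE has apparent accuracy 0.375 + 0.450 = 0.825, which is simply the true accuracy of Gd (0.5×0.75 + 0.5×0.90).

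**Step 4. What 100 pairs can deliver for agreement.** If all 100 pairs are usable, the 95% CI half-widths, in SDs of the paired differences, are:
- mean difference: t(0.975, 99)/√100 = 1.984/10 = 0.198;
- each limit of agreement: 1.984 × √(1/100 + 1.96²/(2×99)) = 0.340.

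**The case against.** The best defence is that the gold-standard label is loose wording. Read with the Background objective, it may mean only that Gd-DCE is the established comparator for permeability, in which case the planned comparison is coherent and the fault lies in an overambitious Abstract. The protocol also never defines superiority or effectiveness as sensitivity or specificity, so the zero-probability statement applies only if accuracy is scored against Gd.

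Both points are fair, and the second limits how Steps 1 and 3 should be read. Neither rescues the Hypothesis. If Gd-DCE is merely the comparator, some other source of truth is needed to say which scan diagnoses better, and the readable text names none. Step 2 does not depend on accuracy scoring at all.

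An unseen SAP might add analysis detail. But the purpose, the hypothesis and the reference are fixed in the protocol itself, and they conflict there. The figure not reproduced could in principle carry more information, but it would not remove the conflict between the quoted statements.

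**Conclusion.** The concern holds, with high confidence, and needs correcting. The protocol carries two aims and its reference fits only one of them. Feasibility and comparison with Gd-DCE can be met; better diagnosis than gadolinium imaging cannot be shown. With Gd-DCE as the reference, the chance of demonstrating better DGE accuracy is exactly zero whatever the sample size; with Gd-DCE as a mere comparator, the stated measures and tests still cannot say which scan is right. The same gap affects the grade and infiltration aims, which have no reference. This conclusion rests on the quoted text and on no independent reference appearing in the readable protocol; it does not depend on the assumed accuracy figures, which only illustrate it.

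**What to change.** **Preferred: bring the Abstract into line with the Background.** Restate the Purpose and Hypothesis as feasibility of DGE and its agreement with Gd-DCE, and delete the claims of superiority and greater effectiveness. Report the paired difference in hyperintense area with a 95% CI, together with limits of agreement or an ICC. State explicitly that hyperintense area is measured on the Gd-DCE images too, and how, since the Measure entry does not spell this out. Label the grade and infiltration aims exploratory, and draw no conclusion on them from the gadolinium comparison. The cost is a protocol amendment, which Ethical considerations requires the ethics committee to approve first, a defined Gd-DCE measurement, and a more modest claim. No new patient procedures are needed.

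**Alternative, only if superiority is kept.** Remove the gold-standard role from Gd-DCE and score both scans against a reference independent of both, such as routine pathology where it exists and can be matched to the image region. This also requires:
- a positivity rule for each scan, because the measures are continuous;
- regions that include non-tumour tissue, because every participant enters with a mass and specificity could not otherwise be estimated;
- a paired analysis that allows for clustering of regions within patients, for example GEE or a patient-level bootstrap;
- no claim that routine pathology alone validates the extent of infiltration.

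This option adds image-to-tissue matching work and restricts the comparison to patients and regions with matched pathology. The protocol gives no basis for estimating how many of the 100 would remain.
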